## IMPORTANT REMINDER

**Any changes to the study must be included in a modification submission, including but not limited to:**

- Any changes to the **study title or purpose of the research**,
- Any changes to the **number of subjects or target subject population**, including but not limited to age, race, disability status, and gender,
- Any changes to **currently approved study procedures, recruitment materials, informed consent process or forms, or surveys/interview guides/assessments**.

***Make your changes in the appropriate sections of the IRB protocol application smartform, including replacing any attachments (e.g. recruitment materials, consent forms, surveys/interview guides/assessments, etc.) being updated.***

---

\*required

### Modification Summary

---

**Briefly describe the proposed modification(s) and explain why each change is needed.**

I am seeing increased interest in my study, so to be safe I would like to increase the study sample size from 60 to 100. Given the benefit of the intervention and interest from the eligible community members, it seems fair to increase the sample size and not exclude any interested eligible members.

I am also increasing focus group number. We will ask for 8- 10 volunteers and divide them into two groups of 4-5 participants. As the sample size increases, I would like to make sure that focus group is representative of the sample as well, so I would like to increase focus group participants.

These changes have been made in the protocol as well.

\*required

### Assessment of Risk

---

Indicate whether the proposed modification increases risk to participants enrolled in this study.

This modification **does not** increase risk to participants enrolled in this study.

This modification **does** increase risk to participants enrolled in this study.

## About Cayuse Submission System

---

The Cayuse submission system is an interactive web application. As you answer questions, new sections relevant to the type of research being conducted will appear on the left-hand side. Therefore not all numbered sections may appear.

Additional information has been added throughout the form for guidance and clarity. That additional information can be found by clicking the question mark at the top-right corner of each section.

You do not have to finish the application in one sitting. **Be sure to click the "Save" button periodically.**

## UNLV IRB

---

- You must have a formal approval letter from the IRB before beginning data collection.
- The Social and Behavioral IRB meets on the first Thursday of each month and the Biomedical/School of Medicine IRB meets on the third Tuesday of each month. Applications that need review by the Board should be submitted at least four weeks prior to the meeting.
- Protocols are reviewed in the order they are received.

## Information to have available

---

- Study Recruitment Document(s)
- Detailed Study Information
- Consent Form(s)
- Questionnaires, Interview Guides, and other Data Collection Instruments
- Facility Authorization/Acknowledgement Letters

- Agreements (IRB Authorization Agreements, Volunteer Agreements, Data Use Agreements, etc.)
- Funding and/or Sponsor Information

\*required

**I have read the information above and I am ready to begin my submission.**

---

Yes

## Is this human subjects research?

\*required

Does your proposed project fit the definition of "research" defined as a "systematic investigation, including research development, testing and evaluation, designed to develop or contribute to generalizable knowledge"?

---

Yes

No

\*required

Does your proposed project include activities using "human subjects" defined as a "living individual about whom an investigator (whether professional or student) is conducting research"?

---

Yes

No

\*required

Is this a multi-institutional/collaborative study?

---

*Multi-institutional/collaborative studies are research conducted in conjunction with an institution or with personnel not affiliated with UNLV.*

Yes

No

## Funding

\*required

Do you have funding for this research study?

---

Yes

No

Pending

## Funding Source

---

*Please search for your funding source. If the sponsor is not found, enter the information in the text field below.*

National Institute of General Medical Sciences

Provide the sponsor if it is not found above.

---

the National Institute of General Medical Sciences, National Institutes of Health under grant number U54 GM104944

\*required

What is the funder type?

---

Federal

State Government

Sponsor

Foundation

Department/College

Other

PLEASE NOTE: Once you obtain additional funding, a modification will need to be submitted.

---

## Key Personnel

---

**NOTE:** If you cannot find a person in the people finder, please contact the ORI-HS Office.

ORI-HS has moved to a "key personnel" model, in which protocols only need to list the PI, Student Researcher (if a student is conducting the research as part of their own capstone/thesis/dissertation), and at least one Primary Contact (this defaults to the individual completing the form, but this can be any individual(s) who need edit/direct access to the protocol application). The PI will be responsible for keeping a record of all research team members and ensuring that all have completed the required CITI training and any other study requirements in a [Research Team Member Log](#) or documented elsewhere in their own study records, which does not need to be submitted to the IRB for review.

Ultimately, it is the PI's decision to decide who constitutes key personnel. However, ANY persons working on the protocol listed must complete CITI training. In addition, it is the PI's responsibility to verify that the training has been completed.

\*required

## **Student Researcher**

---

*Add the student **only** if they are conducting this research to satisfy graduation requirements such as Thesis, Dissertation, Senior Capstone, etc. Only **one** student may be listed here. Additional students can be listed under Primary Contact if they are conducting this research to satisfy graduation requirements.*

Yes

- No

**Note: All study personnel will need to complete the following:**

*The human subject training course: "Social/Behavioral Research" or "Biomedical Research" course offered through CITI. Must be taken within the last five years.*

---

\*required

### **Conflict of Interest**

---

Do you or any investigator(s) participating in this study have a financial interest related to this research project?

---

Yes

No

Does the PI or any member of the research team have an authoritative role over the research subjects (e.g., PI is the instructor of the course being recruited to participate).

---

Yes

No

## Subject Enrollment

---

\*required

**Select the age range of participants that will be enrolled in this study.**

---

*Check all that apply*

fetus

birth to less than 18 years old

18 years and older

\*required

**Describe the different populations that will be recruited and enrolled**

---

*Provide the inclusion/exclusion criteria for each population.*

Loneliness is a serious public health problem that affects more than 35% of older adults. Given that the study is testing an intervention to reduce loneliness and its implications among older adults, we will only include **adults 50 years of age or older**. We will be recruiting adults aged 50 and older living in Southern Nevada.

**Inclusion criteria:** *adults age 50 years or older living in Southern Nevada*

**Exclusion criteria:** *cognitive or language barriers that would be determined by whether they are able to understand and repeat information from informed consent. If we determine they are not able to provide informed consent, they will be excluded from the study.*

\*required

**Maximum number of subjects**

---

*Enter the total maximum number of subjects to be recruited and enrolled*

100

\*required

**Provide the enrollment breakdown number for each participant population**

---

*For example: n= 5 teachers, n = 30 students*

n= 50 intervention, n=50 waitlist control

\*required

**What are the selection criteria for research participants?**

---

**Include sample size calculations, if applicable.**

Adults age 50 years or older, who are willing to participate will be recruited unless they have a significant cognitive or language barrier that will prevent them from successfully answering the study questionnaires.

We will use a randomized controlled trial (RCT) with waitlist control to determine the intervention's feasibility, acceptability, and initial efficacy. Although the proposed study is a feasibility pilot study, we will investigate the preliminary efficacy of the intervention. Therefore, the sample size for this current pilot study was estimated based on four repeated measurements: (baseline, right after intervention, post-intervention (at one month), and follow-up (at second month). Using an estimated effect size (Cohen's  $f= 0.2$ ), an alpha of 0.05, and a power of 90%, for a repeated measure ANOVA between-within effects, with two groups and four measurement time points, the sample size was determined to be 46. This sample size was then increased by 33% to allow for attrition, to give the total sample of 60. The sample size was determined using G\*Power (v. 3.1.9.7).

**Given the interest from the community, we are increasing our sample size to 100. We do not want to exclude eligible community members who might benefit from participating in the study. This will help increase the study power as well.**

\*required

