## **Objectives**

---

*Briefly describe your research questions and the objectives of this study in lay terms. State what you hope to learn from the study and assess the importance of this new knowledge. What do you aim to achieve through this research?*

**Note:** DO NOT copy and paste directly from your grant proposal, dissertation prospectus, clinical protocol, etc.

Objective 1: To evaluate the feasibility of implementing loving-kindness meditation (LKM) among older adults. Research Question 1: Is LKM intervention feasible and acceptable among older adults? We hope to find that intervention is feasible and acceptable among this population. We will also gather data on challenges and how to improve/refine this intervention for future research through a focus group interview.

Objective 2: To examine the preliminary effectiveness of the LKM in increasing positive emotions such as compassionate love. Research Question 2: What is the preliminary effect of the LKM on compassionate love? Hypothesis: Older adults will show an increased compassionate love (Self-compassion scale) after 30 days of intervention. Objective 3: To examine the preliminary impact of the LKM in reducing loneliness and improvement in cognitive function and mental health. Research Question 3: What is the preliminary effect of the LKM on loneliness, depressive symptoms, anxiety scores, and cognitive function?

Hypothesis: Older adults will show a reduced feeling of loneliness, depressive symptoms (CESD) and anxiety (PROMIS anxiety scale), and improved cognitive function (PROMIS cognitive function scale) after 30 days of intervention.

\*required

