Except for demographic information, other data and some intervention evaluation questions will also be collected at the end of the intervention, at 4 week and 8 week. There will be one extra data collection for control group before they get their intervention at 4 week. If for any reason participants refuse to participate during any part of the study, we will collect the reasons for their premature dropping out of the study. Some of the questions that will be asked to those who drop out of the study prematurely are in "Guide for Quantitative Data Collection" attachment.

The intervention primarily involves orientation and mindfulness practices such as proper posture, breathing techniques. We will also teach them the importance of the intervention and daily

practices, how to deal with thoughts that may arise during the meditation practice, and encourage them to write about their daily meditation experiences in the diary provided to them. We will also teach them loving-kindness meditation and provide them with guided meditation on an MP3 device, which they do not have return upon completion of the study. The orientation and intervention will happen in the lobby area, common space, or OLLI classroom in a group setting. The LKM recording will consist of mindfulness practice where they are guided to focus on compassion and kindness for themselves and others. Recording for both brief orientation and LKM are attached. After intervention session is over, participants are encouraged to practice guided meditation daily using the mp3 device for 20-25 minutes on their own at time appropriate for them. They will be encouraged to write their experience in the diary after the practice, which can take from 5 to 10 minutes daily. The diary will be a small folder with some questions to guide their entries daily. Please see dairy or journal requirement attachment for more information. The diary will be given to the participants after the intervention training. There will be weekly reminders via phone call to practice meditation daily and write their experiences in the diary. Weekly call will be around 5-10 minutes weekly for four weeks.

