The orientation is about 10-20 minutes (with both in person and recording) and recorded LKM training is about 30-35 minutes (video links provided under interview section as attachments). We will also have a Questions and Answers session, which could take up 10-20 minutes. Participants will be then given the link to fill out the post intervention questionnaires on their own and if they request paper and pen version, those would be available as well.

After 3 weeks of intervention, we will call to set up an appointment to meet both intervention and control group to collect data for 4 week data collection. At this data collection session, we will also collect 30-day journal folders. At this time, we will also ask for **8-10** volunteers for focus group study (we will have two group of 4-5 participants) and once we have their permission, we will set up another appointment for focus group interview, which may take up to 90 minutes at either OLLI campus or apartment's media room. We will also set up an appointment for control group for their LKM training after collecting time 2 data from them. We will do a month follow-up again at 8 week for intervention group and 4week post-intervention data collection for control group.

There are three areas of outcome measures we are aiming to determine: feasibility, acceptability, and initial efficacy:

(1) feasibility of collecting measures of self-compassion, loneliness, depressive symptoms, anxiety, and cognitive function; (2) acceptability of the intervention (i.e., satisfaction, adherence, recruitment, and retention rates); and (3) initial efficacy (i.e., changes in loneliness along with self-compassion, depressive symptoms, anxiety and cognitive function at immediately post-intervention, at 30 and 60 day follow-up). We will evaluate feasibility through participants' satisfaction, their continued use of intervention after the study completion, how appropriate the intervention was for them, their positive or negative effects associated with the intervention. We will also assess their active and continual participation, retention rates, participation rate, and missing data on collected measures. We will also conduct two focus group with **4-5 participants in each group** at the end of the study to determine the feasibility of the study and how we can further improve the intervention for future research. PI will transcribe the qualitative interviews.

\*required

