### **Compensation**

---

Will subjects be paid or otherwise compensated for research participation?

---

*NOTE: UNLV has implemented the Forte Research Payments System as the central system to electronically manage incentives for UNLV research participants. The system will pay research participants via VISA credit card, check, or direct account deposit.*

*Please contact [contact] if you have questions about the use of Forte, to begin the process, or want to receive a waiver in order to use an alternative payment method.*

Yes

Describe the amount and nature of any compensation to subjects. Include gifts, research credit, gift cards, etc.

---

Participant Incentives (amount listed is per participants): Intervention Group: \$25 per participants for baseline data collection; mp3 device with micro sd card (total of \$35 value for guided meditation, and they will keep the mp3 device and return it is not expected) after orientation and first intervention training; \$ 10 per participants after LKM intervention training; Post intervention data collection and 30 day diary entries will be compensated with \$30. At one month follow-up data collection, participants time will be compensated at \$20 per participants. Control Group: \$25 per participants for baseline data collection; \$20 per participants after time 2 data collection before intervention. During intervention, mp3 device with micro sd card will be provided. \$10 per participants after LKM intervention training; Post intervention data collection and 30 day diary entries will be compensated with \$30. At one month follow-up data collection, participants time will be compensated at \$20 per participants. Focus Group: \$25 per participants for 90 minutes interview.

No

\*required

Indicate the method of payment.

---

Forte System Gift Card

*The Forte Research Payment System asks for participant identifiers (name, gender, email, mailing address, and date of birth). In the consent form, please include that participants may be asked to provide their name, gender, email, mailing address, and date of birth for compensation purposes. Specify if these identifiers will or will not be linked to their study data.*

---

Research Credit

Other

\*required

When and how is the compensation provided to the subject?

---

*Most studies require partial compensation be given for partial participation. Please address this in your answer.*

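### The stated 90% power is for a two-group, four-occasion ANOVA, but controls are trained after week 4, so only baseline to week 4 is a randomised LKM-versus-no-LKM comparison and its power is not stated

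*Combined protocol and SAP*

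**What the plan says.** The sample-size text (section *Include sample size calculations, if applicable*) lists four occasions: baseline, right after intervention, one month and two months. With Cohen's f of 0.2, alpha 0.05 and 90% power it reports: "for a repeated measure ANOVA between-within effects, with two groups and four measurement time points, the sample size was determined to be 46". This was raised to 60 for attrition and later to 100 (50 per arm) because of community interest. The text says the increase helps power but gives no new calculation.

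The procedures (section *How will you conduct this study?*) describe the control arm as follows:

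- Controls have an additional visit while still untreated: "There will be one extra data collection for control group before they get their intervention at 4 week"
- Their training comes only after that visit: "We will also set up an appointment for control group for their LKM training after collecting time 2 data from them"
- By week 8 both arms have therefore been trained, and the same visit means different things in each: "We will do a month follow-up again at 8 week for intervention group and 4week post-intervention data collection for control group"

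The *Compensation* section confirms the order for controls, with a payment "per participants after time 2 data collection before intervention".

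The *Objectives* hypotheses are set at 30 days, for example: "Older adults will show an increased compassionate love (Self-compassion scale) after 30 days of intervention". The procedures section nevertheless counts change at three times as initial efficacy; its list of outcomes and times ends with "anxiety and cognitive function at immediately post-intervention, at 30 and 60 day follow-up".

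**The concern.** A two-group, four-occasion interaction tests LKM against control only if the control arm stays untreated at all four occasions. Here it does not. The quoted power therefore belongs to a test that does not answer the 30-day hypotheses, and the contrast that does answer them has no power statement.

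Two misreadings could follow. A week-8 arm difference near zero could be reported as no lasting effect, when both arms have by then been trained. And the 90% figure could be attached to the week-4 result, although it was calculated for a different test and a different sample size.

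**Working it through.** **1. Which occasions compare LKM with no LKM**

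| Occasion | Intervention arm | Control arm | What the arm difference measures |
|---|---|---|---|
| Baseline | untreated | untreated | chance imbalance |
| Right after intervention | just trained | no untreated measurement planned | no randomised counterpart |
| Week 4 | 4 weeks after training | untreated (time 2) | LKM versus no LKM |
| Week 8 | 8 weeks after training | 4 weeks after training | immediate versus delayed LKM |

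Lining the arms up by time since their own training does not help, because both arms are then treated at every post-training occasion. If the benefit is B at both 4 and 8 weeks after training, the expected week-8 arm difference is B − B = 0.

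**2. Reproducing the plan's 46**

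Inputs from the sample-size section: f = 0.2, alpha 0.05, k = 2 groups, m = 4 occasions. Assumed, because not stated: correlation ρ = 0.5 and sphericity.

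Within-between interaction F test: λ = f²·N·m/(1 − ρ), df1 = (k − 1)(m − 1), df2 = (N − k)(m − 1).

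- N = 46: λ = 0.04 × 46 × 4 / 0.5 = 14.72, df 3 and 132, power 90.3%.
- N = 44: power 88.8%.

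So 46 reproduces, but only with that unstated correlation. The same formula needs 64 at ρ = 0.3 and 28 at ρ = 0.7.

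**3. What f = 0.2 means at week 4**

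f is the SD of the interaction cell effects divided by the outcome SD.

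- Two occasions, arm differences (0, d): f = √(0.5d²/2/4) = d/4, so f = 0.2 is d = 0.80 SD.
- Four occasions, arm differences (0, d, d, d): f = √(0.75d²/4/4) = 0.2165d, so f = 0.2 is d = 0.92 SD.

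The same f therefore implies a different SD effect once the number of occasions changes.

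**4. Power for the baseline-adjusted week-4 contrast**

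Two-sided alpha 0.05, residual SD √(1 − ρ²), noncentrality d/√(1 − ρ²) × √(N/4), df N − 3. For example, d = 0.8, ρ = 0.5, N = 100 gives 0.8/0.866 × 5 = 4.62 and power 99.6%.

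Completers: 100 with no loss. Going from 46 to 60 implies a loss of 1 − 46/60 = 23.3%, and 100 × 46/60 = 76.7, taken as 76.

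| ρ (assumed) | N for 90% power, d = 0.8 | Power, N = 76 | Power, N = 100 | Detectable at 90%, N = 76 | Detectable at 90%, N = 100 |
|---|---|---|---|---|---|
| 0.3 | 62 | 95.0% | 98.6% | 0.72 SD | 0.63 SD |
| 0.5 | 52 | 97.8% | 99.6% | 0.65 SD | 0.57 SD |
| 0.7 | 36 | 99.8% | >99.9% | 0.54 SD | 0.47 SD |

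**5. Does the 90% carry over at N = 46?**

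At ρ = 0.5 the adjusted week-4 analysis has 86.5% power for 0.80 SD and 94.2% for 0.92 SD. The stated figure lies between the two, so it may overstate or understate the week-4 power, depending on how f is translated.

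**The case against.** The strongest reply is that the loss of power is small or absent. N = 46 is no longer the planned size. With baseline adjustment, the week-4 contrast at 46 has 86.5% or 94.2% power depending on the effect mapping, and at 100 it is above 90% for the stated f across the correlations tried. This stands. A reader might infer that the trial is underpowered, perhaps from the 75.6% that an unadjusted change analysis gives at N = 46 with f held at 0.2. That inference is not supported. The figure fixes f while the number of occasions falls, which lowers the implied difference from 0.92 to 0.80 SD. It also uses an analysis less efficient than baseline adjustment, at a sample size that has been superseded.

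A second reply is that the plan never says the 60-day change is an LKM-versus-control effect. It lists changes at three times, sets its hypotheses at 30 days, and already collects the untreated week-4 control data. This also stands. A reader might infer that the sponsor intends an invalid 60-day claim, but the text is only silent on which comparison is meant.

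Third, the text reviewed is an IRB application. The schedule of assessments is an attachment not reproduced, and the modification summary says "These changes have been made in the protocol as well", which may point to a separate document. Either could name the week-4 contrast, so it cannot be said that the contrast is named nowhere. Neither could change the fact that controls are trained by week 8.

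Finally, this is a feasibility pilot with preliminary efficacy as its second aim. That limits the weight of the point but does not make the power statement match the design.

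**Conclusion.** The point holds as a mismatch between the power statement and the design. The four-occasion interaction is not a test of LKM against no LKM. Only baseline to week 4 is, and the text provided gives no power for it at 46, 60 or 100. Week 8 is immediate versus delayed LKM.

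The consequence is for what may be claimed, not for whether the sample is large enough. With 76 to 100 completers, power for a 0.8 SD week-4 difference is 95.0% or more at correlations of 0.3 to 0.7. However, 0.8 SD is what f = 0.2 means on two occasions, and the plan does not say so. Differences below about 0.57 SD (100 completers) or 0.65 SD (76) have less than 90% power at a correlation of 0.5.

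These figures assume the correlation, two-sided testing of one outcome at 0.05, equal arms, and loss as implied by the step from 46 to 60.

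**What to change.** Three changes of wording in the sample-size and procedures sections:

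1. State that the randomised efficacy comparison is the between-arm difference at week 4, adjusted for baseline, with data collected before the control arm receives LKM.
2. State that the week-8 arm comparison is immediate versus delayed LKM, not a 60-day LKM-versus-control effect, and that measurements right after training are described within arm.
3. Replace the power text with figures for the analysis in item 1, for example: *Power is for the baseline-adjusted week-4 comparison of two equal groups, two-sided alpha 0.05; the correlation between baseline and week 4 is assumed. An f of 0.2 on two occasions is a 0.8 SD between-arm difference. Ninety per cent power for it needs 52 completers at correlation 0.5 (62 at 0.3, 36 at 0.7). With 100 and 76 completers, power is 99.6% and 97.8% at 0.5 (98.6% and 95.0% at 0.3). The difference detectable with 90% power is 0.57 and 0.65 SD at 0.5 (0.63 and 0.72 SD at 0.3; 0.47 and 0.54 SD at 0.7).*

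If the schedule of assessments or a separate protocol already names a contrast, align it with item 1.

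Cost: no added participants, visits or measurements. The downside is that 60-day results can no longer support an LKM-versus-no-LKM claim.

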Then, participants' baseline data for screening will be collected before randomization. Randomization will be done based on participants race, gender and socio-economic statuses resulting with comparable demographic status in both intervention (n=50) and control group (n=50). Baseline data includes questionnaire on demographic information and measures of loneliness, depressive symptoms, anxiety, self-compassion, and cognitive function (see attached Study questionnaires LKM). The baseline data collection will occur one on one in a common private space in the apartment or OLLI classroom to protect participants privacy and for research staff safety. To further strengthen our staff's safety, they will travel in pairs to collect data and provide intervention. Participants will fill out the questionnaire on their own using either their own smart phone, paper and pen (for which data will be transferred to Qualtrics), or research iPad (however, study ID section will be entered by the research staff and participants are asked to fill out rest of the questionnaire). Our research staff will be there to answer any questions participants may have. We will offer rest/break periods as needed during the data collection sessions. Data will be collected using Qualtrics software, which will be password protected, which will ensure the protection of the participants' data. We may use paper pencil for data collection when needed and transfer the data to Qualtrics. We will destroy the paper data once the data has been cleaned and ready for analysis. The paper questionnaire will have Study ID section same as Qualtrics and personal data will not be collected during baseline or other data collection session. The only time personal information is collected during participants sign up, and this information will be safely locked in PI's office cabinet and will only be used to contact participants for future data collection sessions.

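### Comparing week-4 scores adjusted for baseline would give a somewhat narrower interval than the four-time ANOVA, the only efficacy test named, and needs no new data

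*Combined protocol and SAP*

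**What the plan says.** The section on sample size calculations describes "four repeated measurements: (baseline, right after intervention, post-intervention (at one month), and follow-up (at second month". It sizes the trial "for a repeated measure ANOVA between-within effects, with two groups and four measurement time points", using Cohen's f = 0.2, alpha 0.05 and 90% power. The result is 46 participants, raised to 60 for attrition and later to 100 (50 per arm). No other efficacy model appears in the documents.

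Under Objectives, the hypotheses are set at 30 days: "Older adults will show an increased compassionate love (Self-compassion scale) after 30 days of intervention" and "Older adults will show a reduced feeling of loneliness, depressive symptoms (CESD) and anxiety (PROMIS anxiety scale", with cognitive function alongside.

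Under the study-conduct heading (How will you conduct this study?):
- "baseline data for screening will be collected before randomization", and "Baseline data includes questionnaire on demographic information and measures of loneliness, depressive symptoms, anxiety, self-compassion, and cognitive function". Every efficacy outcome therefore has a pre-randomisation value.
- "There will be one extra data collection for control group before they get their intervention at 4 week". Controls are trained only after that measurement.
- The immediate questionnaire is completed after the training session.
- Week 8 is a further follow-up for the intervention arm, and the 4-week post-training assessment for controls.

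**The concern.** Week 4 is the only follow-up that sets trained participants against untrained ones. At the immediate assessment controls have no concurrent untreated score, and by week 8 both arms have been trained. Week 4 also matches the 30-day hypotheses.

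In a four-time ANOVA baseline is a response, so the group difference from baseline to week 4 is a difference in change scores. Subtracting the whole baseline value adds noise unless baseline and week 4 are very highly correlated. Using baseline as a covariate removes only the part that predicts week 4.

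What is at stake is the width of the week-4 interval, which is the most useful efficacy output of a pilot. Bias is not at issue.

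**Working it through.** **Inputs from the documents.** f = 0.2, alpha 0.05, 2 groups, m = 4 times, N = 46 before attrition, current N = 100, equal arms, 33% inflation for attrition.

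**Assumptions.** The documents do not give the correlation ρ between scores, so 0.3 to 0.9 is shown. Compound symmetry, sphericity and complete four-visit data are assumed. Completers: 1 − 1/1.33 ≈ 25% loss, so 100 becomes 75.

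**Step 1: reproduce the planned sample size.** In the G\*Power within-between form, λ = f²·N·m/(1−ρ), with 3 and 3(N−2) degrees of freedom. At ρ = 0.5:
- N = 46: λ = 0.04 × 46 × 4/0.5 = 14.72 on 3 and 132 df, power 0.903. N = 44 gives 0.888, so 46 is reproduced.
- N = 75: λ = 24, power 0.990.
- N = 100: λ = 32, power 0.999.

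**Step 2: the effect that f = 0.2 represents.** Take a constant difference of d SD at all three times after baseline. The time profile (0, 1, 1, 1) has variance 0.1875, so f² = 0.1875·d²/4 and d = 0.2/0.2165 = 0.92 SD.

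**Step 3: half-width of the 95% interval at week 4, in SD of one score.**
- ANOVA contrast (week 4 minus baseline, pooled error): t(0.975, 3(N−2)) × √[2(1−ρ)·4/N].
- ANCOVA with p covariates: t(0.975, N−2−p) × √[(1−ρ²)·(4/N)·(1 + p/(N−p−3))]. Here p = 1 for baseline alone, and p = 6 for baseline plus five covariates unrelated to outcome.

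Worked case, N = 100 and ρ = 0.5:
- ANOVA: 1.968 × √(1 × 0.04) = 0.394.
- ANCOVA, baseline only: 1.985 × √(0.75 × 0.04 × (1 + 1/96)) = 0.346, which is 12.2% narrower.

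| N | ρ | ANOVA | Baseline only | Narrower by | Plus five covariates | Narrower by |
|---|---|---|---|---|---|---|
| 100 | 0.3 | 0.466 | 0.381 | 18.3% | 0.391 | 16.0% |
| 100 | 0.5 | 0.394 | 0.346 | 12.2% | 0.355 | 9.8% |
| 100 | 0.7 | 0.305 | 0.285 | 6.5% | 0.293 | 3.9% |
| 100 | 0.8 | 0.249 | 0.239 | 3.8% | 0.246 | 1.2% |
| 100 | 0.9 | 0.176 | 0.174 | 1.2% | 0.179 | −1.6% |
| 75 | 0.3 | 0.539 | 0.442 | 17.9% | 0.459 | 14.7% |
| 75 | 0.5 | 0.455 | 0.401 | 11.8% | 0.417 | 8.4% |
| 75 | 0.7 | 0.353 | 0.331 | 6.1% | 0.344 | 2.5% |
| 75 | 0.8 | 0.288 | 0.278 | 3.4% | 0.289 | −0.4% |
| 75 | 0.9 | 0.204 | 0.202 | 0.7% | 0.210 | −3.1% |

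**Step 4: simulation check.** With 4,000 runs per cell and the four-visit ANOVA fitted, baseline-only gains at N = 100 were 18.2%, 12.2%, 6.8%, 4.0% and 1.2% across the same correlations. This agrees with the formulas.

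**Step 5: what the gain is worth.** Width falls roughly as 1/√N. Matching a 12.2% narrowing by recruitment would therefore need about 1/0.878² = 1.30 times as many participants.

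**The case against.** **The ANOVA is named only for sizing.** The documents never say outright that it will be the final analysis, and an analysis plan may exist elsewhere. That is a fair limit on the claim. But no other efficacy model is stated in what was supplied, and if the ANOVA is not the intended analysis, the proposed sentence fills that gap.

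**The comparator is constructed.** The 3-df interaction test gives no single interval, so the comparison must use its week-4-minus-baseline contrast. Against the average of all three times after baseline, the single-time adjusted interval is wider once ρ exceeds 1/3. At N = 100 and ρ = 0.5 it is 0.346 against 1.968 × √((4/3) × 0.5 × 0.04) = 0.321 SD. The arithmetic is correct, but that average is a different quantity, because it includes times at which controls are trained or have no untreated score.

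**The gain is uncertain and can vanish.** This stands. It shrinks as ρ rises. With five uninformative covariates it is gone between 0.8 and 0.9 at N = 100, and by about 0.8 with 75 completers.

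**Power is comfortable only for a large effect.** This also stands. The 0.990 and 0.999 rest on f = 0.2, about 0.92 SD. For a constant 0.5 SD at ρ = 0.5, λ is 7.03 and 9.375, and four-time power is about 0.58 and 0.72 at N = 75 and 100.

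**Naming week 4 as the main time goes beyond precision.** It does, but the choice follows from the stated 30-day hypotheses and the waitlist timing, not from the width calculation.

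**Conclusion.** The concern holds, at low severity. Both analyses are unbiased at week 4 under randomisation, and the stated power is not threatened on the plan's own f = 0.2 with ρ = 0.5: at 75 completers, week-4 power is 0.978 for the ANOVA contrast and 0.995 for ANCOVA. What is lost is precision. Across assumed correlations from 0.3 to 0.9, the baseline-adjusted interval is narrower by roughly 18% down to 1%, whether 100 or 75 participants contribute. At 0.5 the gain is about 12%. These sizes rest on the assumed correlations, compound symmetry and complete data. The direction for baseline-only adjustment is secure at these sample sizes unless the correlation is near 0.9 or above, where the two methods are practically equal.

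**What to change.** Keep the ANOVA sentence as the basis of the 46, and add, before outcome data are examined:

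*For each outcome, the main efficacy analysis compares week-4 scores (for controls, the measurement before their training) between arms as assigned, by ANCOVA adjusted for the baseline value of that outcome. It includes all randomised participants with a week-4 score, whether or not they attend other visits, and reports the adjusted mean difference with its 95% confidence interval.*

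Report the immediate and week-8 changes as secondary, and not as trained-versus-untrained comparisons.

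The study-conduct section says "Randomization will be done based on participants race, gender and socio-economic statuses resulting with comparable demographic status in both intervention". Adjusting for those factors as well would be consistent with the allocation. If they are unrelated to outcome, however, it uses up part of the gain, so it fits better as a supporting analysis with the categories written down beforehand.

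The cost is one sentence and one degree of freedom. No new data are needed, since every outcome is already collected before randomisation and at week 4 in both arms.
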